### **10.3.2. Day of Procedure**

< Visit 2>

Subjects who meet all criteria for the inclusion • exclusion will be admitted to the hospital on the day before the procedure in accordance with the clinical standard of the institution and will undergo the EUS -guided transluminal drainage using the SPAXUS stent. The following procedure shall be

performed on the day of the procedure and the subject should stay in the hospital for at least one day or more after the procedure for observation of the progress.

- Vital Signs (Blood pressure, Pulse rate, Respiration rate, Body temperature)
- EUS-guided transluminal drainage with Niti-S SPAXUS™ Stent
- Laboratory tests (Hematology, Coagulation, Chemistry)
- Clinical symptoms
- Radiological Examination (X-ray: abdomen)
- Concomitant Medications /Procedures
- Adverse Events /Serious Adverse Events

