#### **10.3.3. Follow-Up Observation**

< Visit 3>

After the procedure of the Niti-S SPAXUS™ Stent, the subjects will be observed for the post-procedure treatment and progress in accordance with the clinical standard of the institution. On the following day of the procedure (Day 2), the investigator will confirm the location and deployment state of the stent and the stent lumen patency through clinical symptoms, laboratory tests and radiological examination, and evaluates the clinical symptoms and the adverse events. Then, the following procedures will be performed.

- Vital Signs (Blood pressure, Pulse rate, Respiration rate, Body temperature)
- Physical Examination
- Laboratory tests (Hematology, Coagulation, Chemistry)
- Clinical symptoms
- Radiological Examination (X-ray: abdomen)
- Concomitant Medications /Procedures
- Adverse Events /Serious Adverse Events

< Visit 4>

Subjects enrolled in this study will have a follow-up visit at the time of discharge (Day 5 ± 2 days) and the following procedures will be performed at the visit.

- Vital Signs (Blood pressure, Pulse rate, Respiration rate, Body temperature)
- Physical Examination
- Laboratory tests (Hematology, Coagulation, Chemistry)
- Clinical symptoms
- Radiological Examination (X-ray: abdomen)
- Concomitant Medications /Procedures
- Adverse Events /Serious Adverse Events

< Visit 5>

At Day 30 ( $\pm$  10 days) after the procedure, abdominal CT scanning will be performed to confirm the resolution of the pancreatic pseudocyst which is the primary effectiveness endpoint of the study, and to assess the clinical success. If the subject meets the criteria for stent removal through such as laboratory tests, clinical symptoms and abdominal CT scanning by the judgement of the investigator, the stent will be removed using an endoscope and the following procedures will be performed.

- Vital Signs (Blood pressure, Pulse rate, Respiration rate, Body temperature)
- Physical Examination
- Laboratory tests (Hematology, Coagulation, Chemistry)
- Clinical symptoms
- CT Scanning (abdominal CT)
- Removal of Niti-S SPAXUSTM Stent (using endoscopy)
- Evaluation of clinical success
- Evaluation of the stent removal success
- Concomitant Medications /Procedures
- Adverse Events /Serious Adverse Events

< Visit 5-1>

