### 12.2. Definition of Serious Adverse Event /Adverse Device Effect

Serious Adverse Event /Adverse Device Effect refers to the adverse events or adverse device effects occurred due to the investigational device, which is applicable to any of the following consequences.

- ① Resulted in death or life threatening
- ② Required inpatient hospitalization or prolongation of existing hospitalization
- ③ Resulted in persistent or significant disability/incapacity
- ④ Caused a congenital anomaly/birth defect

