### 14.2.3. Analysis of Safety Evaluation

The safety evaluation variables such as the frequency and percentage of stent rupture, re-operation, reoperation, procedure or medical device related serious adverse events and deaths are presented, and a summary by each subject is described.

The descriptive statistics (number of cases, mean, standard deviation, median value, maximum and minimum values) are presented for the continuous variables such as all adverse events, vital

signs, and physical examinations collected from the subjects. The changes of post-stent application compared to pre-stent applications will be analyzed by using Paired t-test or Wilcoxon signed-rank test for continuous variables, and McNeamar's test for categorical variables. The adverse events are classified by using MedDRA and these cases are reported using 'Preferred term' and 'System organ class'. All adverse events are presented by the frequency (percentage) by subjects and the number of subjects. When calculating the subject frequency, if multiple cases of same adverse event occur in one subject based on 'Preferred term' and 'System organ class', it will be considered as one case. Whereas the severity and the causality differ for the same adverse event, it will be processed as the maximum severity and causality. The total number of subjects is used in calculating the subject percentage, and when calculating the number of cases, the case like the one mentioned above will be regarded as different adverse events.

For subjects experiencing the adverse event (or adverse device effect) at least one or more, the subject frequency and percentage will be presented and also a 95% confidence interval will be provided. In addition, for the serious adverse events and the subjects dropped-out of the study due to them, the frequency and percentage of subjects should be presented and listed.

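### Section 12.2 has no seriousness criterion for events that needed intervention, so a complication repaired within the in-patient stay can fall outside the related-SAE rate

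*Combined protocol and SAP*

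**What the plan says.** Section 12.2 lists four seriousness criteria:

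1. death, or a threat to life;
2. "Required inpatient hospitalization or prolongation of existing hospitalization";
3. a disability or incapacity that is lasting or significant;
4. a birth defect.

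The list ends there, and no other safety section adds a criterion. The lead-in to the list says that the term "refers to the adverse events or adverse device effects occurred due to the investigational device".

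On time in hospital, section 10.3.2 admits subjects the day before the procedure and then says that "the subject should stay in the hospital for at least one day or more after the procedure". Section 10.3.3 says that subjects "will have a follow-up visit at the time of discharge (Day 5 ± 2 days"), which is Day 3 to Day 7. The study schedule marks Visits 2, 3 and 4 and the removal visits (5 and 5-1) as in-patient and Visit 6 as out-patient. No length of stay is given for the removal admission.

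SAEs related to the procedure or the stent are the first-listed safety endpoint (sections 11.2.1 and 11.2.2). The synopsis has them reported as frequency, percentage and 95% confidence interval. Section 12.5.2 requires serious events to reach the sponsor within 24 hours, whatever their relation to the device.

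**The concern.** Both device procedures happen while the subject is already admitted, so a complication during placement or removal cannot qualify through a new admission. It has to qualify as life-threatening, as disabling, or as having prolonged the stay. Section 12.6.1 lists bleeding, perforation and stent migration as expected both during and after placement, and these may be repaired on the spot. If the repair works and the subject goes home within the usual window, no criterion clearly applies, even though without the repair the outcome might have been serious.

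What is at stake is the leading safety rate of a pivotal device study, the speed of reporting to the sponsor, and consistency across six centres that may classify the same event differently.

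**Working it through.** **Denominator.** The plan's own figure reproduces. Inputs from section 9.2: one-sided 2.5%, power 80%, expected and reference rates both 96%, margin 0.10.

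n = (1.960 + 0.842)² × 0.96 × 0.04 / 0.10² = 30.14, rounded up to 31. With 10% withdrawal, 31 / 0.90 = 34.4, rounded up to 35. I take 35 as the Safety Set, assuming that the procedure is attempted in everyone recruited.

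**Does a repaired event meet a criterion?** Take a bleed controlled endoscopically during the placement stay, not life-threatening and leaving no lasting disability.

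- Criterion 1: not met, by assumption.
- Criterion 2, new admission: not met, because the subject is already in hospital.
- Criterion 2, prolongation: depends on the length of stay used for comparison. Suppose a site planned discharge on Day 3 and kept the subject to Day 6. Against the planned date the stay was prolonged. Against the Day 3 to 7 window it was not. Section 12.2 does not say which applies. For the removal admission there is no stated stay to compare with.
- Criterion 3: not met, by assumption.
- Criterion 4: not relevant.

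Such an event can be classed as an other adverse event without departing from the text.

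**Share of follow-up spent in hospital.** Assume discharge on Day 3 to 7, one in-patient day at removal, removal on Day 30 or 60, and Visit 6 twenty days later.

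- Lowest: (3 + 1) / (60 + 20) = 5%
- Highest: (7 + 1) / (30 + 20) = 16%

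In-hospital time is a small part of follow-up, but it contains both procedures.

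**Effect on the reported rate.** One subject is 1/35 = 2.9 percentage points. Exact (Clopper-Pearson) 95% limits for x of n are the 0.025 quantile of Beta(x, n − x + 1) and the 0.975 quantile of Beta(x + 1, n − x). For x = 0 the upper limit is 1 − 0.025^(1/35) = 10.0%.

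| Subjects counted | Rate | Exact 95% interval |
|---|---|---|
| 0/35 | 0% | 0 to 10.0% |
| 1/35 | 2.9% | 0.1 to 14.9% |
| 2/35 | 5.7% | 0.7 to 19.2% |
| 3/35 | 8.6% | 1.8 to 23.1% |

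Each subject left out lowers the upper limit by about 4 to 5 points. The counts are illustrative; the documents give no rate for events repaired within the stay.

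**Scope of the definition.** The 12.2 lead-in covers events caused by the device. The endpoint in 11.2.2 also counts procedure-related SAEs, and 12.5.2 applies whatever the relation to the device. Section 6.3.2 has the puncture made with a conventional instrument such as an aspiration needle. A puncture-site bleed could therefore be attributed to the procedure alone and fall outside 12.2 even if it met a seriousness criterion.

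**The case against.** Several stronger readings are tempting, and the documents do not support them.

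- *The hospitalisation criterion hardly applies because subjects are in-patients.* Criterion 2 expressly includes prolongation, which is written for people already admitted. New admission applies in full between discharge and removal and again after removal.
- *Before Day 7 an event is serious only if life-threatening.* Prolongation and disability remain available, and a subject discharged on Day 3 and readmitted on Day 5 meets criterion 2.
- *The length-of-stay passages contradict each other.* A minimum stay in 10.3.2 and a discharge window in 10.3.3 are compatible. A stay extended past Day 7 by an event is plainly prolonged. The vagueness lies inside the window and at the removal admission.
- *Section 14.2.3 puts re-operation outside the SAE count.* It says that "stent rupture, re-operation, reoperation, procedure or medical device related serious adverse events and deaths are presented". Deaths stand in the same list and are serious by criterion 1, so separate tabulation does not mean exclusion.
- *The events disappear.* Sections 11.2.2 and 12.5.1 require all adverse events to be recorded and assessed, 14.2.3 tabulates re-operations and gives a 95% interval for subjects with any adverse event, and an independent gastroenterologist reviews the safety data.

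The safety endpoint is also descriptive, with no performance goal, so no planned success decision turns on it. The 15% complication rate in the comparator-stent study of section 6.2 does not size the gap: its named complications include no bleeding or perforation, and it does not say whether the one migration and one dislodgement were repaired within the stay.

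All of this stands and limits the point. None of it supplies an intervention criterion or a reference for prolongation.

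**Conclusion.** The concern holds in a limited form. The definition lacks an intervention criterion, and its prolongation clause is loosely anchored for the two admissions in which the procedures take place. A complication repaired within the stay can therefore be left out of the related-SAE rate, its interval and the 24-hour report. The loss is one of classification and reporting speed, not of recording. Its size is 2.9 percentage points per subject, assuming a Safety Set of 35. The number of such subjects cannot be derived from the documents.

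The mismatch between the device-only lead-in in 12.2 and the wider scope of 11.2.2 and 12.5.2 is a separate inconsistency. It must be resolved as well, or a new criterion would not reach procedure-related events. The change is inexpensive and should be made; the gap does not affect the primary analysis.

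**What to change.** 1. Add a fifth criterion to 12.2: *required endoscopic, surgical or other medical intervention to prevent any of the outcomes in criteria 1 to 3*. Apply it to the endpoint in 11.2.2, the reporting rule in 12.5.2, the analysis in 14.2.3 and the SAE form. An open-ended clause for medically important events is not proposed, because undefined it would add to between-site variation.
2. State one reference for judging prolongation, for example the discharge date planned before the event, and apply it to both the placement and the removal admission.
3. Reconcile the 12.2 lead-in with 11.2.2 and 12.5.2, so that seriousness is defined independently of cause and relatedness to the procedure or the device is then applied for the endpoint.

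The cost is wording in the protocol and on the SAE form, a somewhat higher reported SAE rate, and a few more expedited reports.

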### 12.3. Adverse Event Assessment

#### 12.3.1. Severity Assessment

When an adverse event occurred, it should be reported according to the following severity assessment criteria

- ① Mild  
When the AE easily tolerated and are of minor irritant type causing no loss of time from normal activities (or functions)
- ② Moderate  
When the AE introduce a low level of inconvenience or concern to the participant and may interfere with daily activities

③ Severe

When the AE interrupt the participant's normal daily activities

### **12.3.2. Assessment of the Causal Relationship with the Investigational Medical Device**

A causality for all the adverse events should be assessed by the investigator and properly recorded. Upon the incidence of an adverse event, the investigator shall evaluate the relation with the investigational medical device according to the following criteria.

- ① Definitely related
- ② Probably related
- ③ Possibly related
- ④ Probably not related
- ⑤ Definitely not related
- ⑥ Unknown

### **12.4. Adverse Event Assessment Criteria**

Any undesirable medical findings on the occurrence of symptoms which were not observed before the participation of this clinical study but newly occurred shall be classified and assessed as adverse events. Expected adverse events will be classified the adverse events and the severity of them shall be classified as to mild, moderate and severe. They will be reported by using the terms based on the 'Preferred Term' and the 'System Organ Class' of MedDRA.

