### 10.2.2. Clinical symptoms

The clinical symptoms will be checked at every visit from the baseline and the following items will be included as the pancreatic pseudocyst-related symptoms.

- Abdominal Pain
- Nausea
- Vomiting
- Anorexia
- Diarrhea
- Others (e.g. fever, a tender mass in abdomen)

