## 12. SAFETY ASSESSMENT CRITERIA INCLUDING ADVERSE EVENTS/ ASSESSMENT METHOD AND REPORTING METHOD

### 12.1. Definition of Adverse Event /Adverse Device Event

- ① An "Adverse Event (AE)" refers to any untoward medical occurrence, unintended disease or injury, or untoward clinical signs (including abnormal laboratory findings) in subjects, users or other persons, whether or not related to the investigational medical device
- ② "Adverse Device Event (ADE)" refers to any harmful and unintended event caused by or associated with the investigational medical device, which undeniably has the causal relationship with the investigational device.
- ③ "Unanticipated Adverse Device Effect" refers to any pattern or the risk extent of the adverse device event, which is not consistent in reflection to the medical device related information available such as the description in the investigator's brochure(IB) or the supplementary to the device.

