### **12.5. Reporting Method of Adverse Event**

#### **12.5.1. Reporting of Adverse Event**

The investigator is responsible to make assessment of all adverse events occurring during the clinical study period and to record them in the case report forms. All adverse events are to be analyzed in the clinical study report and will be assessed.

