### **12.6. Expected Adverse Events and Precautions for Use**

#### **12.6.1. Expected Adverse Events**

< Expected Adverse Events during the procedures of the Niti-S SPAXUSTM Stent >

- Bleeding
- Stent misplacement
- Inadequate expansion
- Stent migration
- Pain
- Perforation

< Expected Adverse Events after Deployment of the Niti-S SPAXUSTM Stent >

- Bleeding
- Pain
- Perforation
- Stent misplacement
- Stent migration

- Stent occlusion
- Fever
- Pancreatitis
- Abscess formation
- Vomiting
- Pneumoperitoneum
- Intraperitoneal leakage
- Peritonitis
- Hematoma
- Inflammation
- Infection
- Fistula
- Ulceration
- Sepsis
- Rupture of intracystic artery
- Stent removal failure

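### Section 12.4 words the adverse event criterion as new onset, which is narrower than 12.1, and nothing says whether worsening of a baseline symptom counts

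*Combined protocol and SAP*

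**What the plan says.** Two sections of the protocol define what counts as an adverse event.

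- **Section 12.1** gives the definition. An adverse event "refers to any untoward medical occurrence, unintended disease or injury, or untoward clinical signs (including abnormal laboratory findings) in subjects, users or other persons", related to the device or not. It has no condition on onset.
- **Section 12.4**, headed as the assessment criteria, says that undesirable findings or symptoms "which were not observed before the participation of this clinical study but newly occurred shall be classified and assessed as adverse events". The sentence after it deals with expected adverse events and their severity grades and carries no onset condition.

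Three other places bear on the point.

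- **Section 10.2.2:** "The clinical symptoms will be checked at every visit from the baseline and the following items will be included as the pancreatic pseudocyst-related symptoms". The list includes abdominal pain, nausea and vomiting, with fever as an example under others.
- **Section 12.6.1** lists pain, fever and vomiting among the expected adverse events after deployment.
- **Section 12.2** builds a serious event from an adverse event or adverse device effect that meets a seriousness criterion, one of which is "Required inpatient hospitalization or prolongation of existing hospitalization".

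No section mentions worsening, aggravation or increased frequency of a symptom present before entry.

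**The concern.** The symptoms a subject may bring into the study overlap with the harms expected from the procedure. Take a subject with mild abdominal pain at screening and severe pain on Day 2. Under 12.1 this is an untoward medical occurrence and can be counted. Under 12.4 read literally, the pain was observed before participation and did not newly occur, so it need not be counted. Six institutions could resolve this differently.

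Both safety endpoints in 11.2.1 (procedure- or device-related serious events, and other adverse events) rest on this classification. So does the proportion of subjects with at least one adverse event, with its 95% confidence interval, in 14.2.3. If worsening is left out, the error goes one way, towards fewer reported harms. In a single-arm study no comparator absorbs it.

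**Working it through.** No figure in the plan depends on this rule, so the check is mainly a comparison of texts.

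**1. Do 12.1 and 12.4 agree?** For a new symptom, both make it an adverse event. For a baseline symptom that worsens, 12.1 can include it. The main sentence of 12.4 does not, and its qualifier on prior observation has no function unless it separates new from pre-existing findings. The two sections differ exactly in the case of worsening.

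**2. Does another section settle it?**

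- Section 12.5.1 obliges the investigator to record all adverse events, which leaves open what an adverse event is.
- Section 12.5.2 requires serious events to be reported within 24 hours whether or not related. But 12.2 defines a serious event as an adverse event or device effect with a serious outcome, so the same classification comes first. The question is practical: Visits 2 to 4 are in-patient visits, and worsened pain that delays discharge would meet the prolongation criterion if it were accepted as an adverse event.
- The maximum-severity rule in 14.2.3 applies only to events already classified as adverse events.
- The before-and-after comparisons in 14.2.3 name vital signs and physical examinations, not clinical symptoms, and no rule turns a change from baseline into an adverse event. If McNemar's test were applied to presence or absence of pain, a subject with pain at both times would be a concordant pair and contribute nothing, however much the pain had worsened.

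None of these settles it.

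**3. What would a missed subject cost?** The denominator is at most the 35 planned subjects. That number follows from 9.2:

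- n = (1.960 + 0.842)² × 0.96 × 0.04 / 0.10² = 30.14, rounded up to 31
- 31 / 0.90 = 34.4, rounded up to 35

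One missed subject is 1/35 = 2.9 percentage points, and slightly more if the Safety Set is smaller.

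**4. How many might be missed?** The documents give neither the proportion with the symptom at baseline (b) nor the proportion of those who worsen (w). As an illustration with assumed values, and with every site applying 12.4 literally, the expected number missed is 35 × b × w:

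| b (assumed) | w = 5% | w = 10% | w = 20% |
|---|---|---|---|
| 30% | 0.5 | 1.1 | 2.1 |
| 60% | 1.1 | 2.1 | 4.2 |
| 90% | 1.6 | 3.2 | 6.3 |

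The range of about 0.5 to 6.3 subjects shows only that the effect could be negligible or material. It is not an estimate.

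**The case against.** The strongest reply is that 12.4 does not exclude anything. It says that new findings are adverse events; it does not say that only new findings are, and it does not override 12.1. Its next sentence brings in expected adverse events without an onset condition, and pain and vomiting are on that list. The English there is too rough to be sure what was meant, but it allows a reading under which worsened pain is counted. A reader might infer from 12.4 that worsening of baseline symptoms is ruled out throughout the study; the documents do not support that. This part of the reply stands, and it limits the point to an inconsistency that sites may resolve in different ways.

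The reply also says that the information is not lost: symptoms are asked about at every visit, Visit 3 has the investigator evaluate symptoms and adverse events together, and an independent gastroenterologist reviews safety data throughout. That is true, and worsening may well be visible in the records. It does not define the numerator of the reported rates. Neither 10.2.2 nor the schedule footnote on symptoms says that symptoms are graded, so a change from mild to severe may not show in the symptom data.

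Finally, safety is analysed descriptively, without a threshold, and the primary endpoint is untouched. This also stands. It bears on the weight of the point, not on whether the two sections should agree.

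**Conclusion.** The point holds as an inconsistency with a possible one-directional effect. Section 12.4 is narrower than 12.1, neither addresses worsening from baseline, and the gap falls on pain and vomiting, which are both baseline symptoms and expected harms. Under-counting occurs only where a site applies 12.4 literally. Its size cannot be derived from the documents; each subject missed is about 2.9 points of 35.

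Three stronger readings go beyond the documents:

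- **That serious events will be missing.** This would require a site to use 12.4 as a filter before applying 12.2. No section exempts a symptom present at baseline, so it is a possibility only.
- **That the population is symptomatic by design.** Inclusion requires a need for drainage, not symptoms. The background in 6.1 speaks of treating symptomatic pseudocysts, so baseline pain is a reasonable expectation, but no rate is given. Fever is a weak example, because active infection requiring antibiotics is an exclusion.
- **That the AXIOS series in 6.2 shows the loss.** Four of the seven complications listed there were pain (three abdominal, one back), but the summary does not say whether that pain existed before the procedure. It also included walled-off necrosis.

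**What to change.** Reconcile 12.4 with 12.1 by rewording the criterion to cover findings or symptoms that *newly occurred, or worsened in severity or frequency compared with baseline*. The comparison can use the symptom checks already made at baseline and at every visit, with the mild, moderate and severe grades of 12.3.1. If the case report form, which is not among the documents, records only presence or absence of a symptom, it would also need a severity entry at each check.

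The cost is one clause and, if needed, that entry. No visit or test is added, and the primary endpoint and sample size do not change. The reported adverse event rate may be slightly higher, because worsening would then be counted at all six institutions.
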